#### 4.7.2.2. Vital Signs

Vital signs will be analyzed for observed value and change from baseline separately for vital signs on injection days and vital signs at each visit (excluding post injection time points on injection days). Refer to [Table 19](#) for the definition of baseline.

In addition, subjects reporting any sponsor-defined PCI vital sign values during the study will be analyzed.

Vital sign values are PCI if they meet both the observed value criteria and the change from baseline criteria. The PCI vital sign values are presented in Table 17 below.

**Table 17: Potentially Clinically Important Vital Sign Criteria**

Parameter	PCI Low	PCI High
Systolic blood pressure	≤90 mmHg and decrease ≥20 mmHg from baseline	≥180 mmHg and increase ≥20 mm Hg from baseline
Diastolic blood pressure	≤50 mmHg and decrease ≥15 mmHg from baseline	≥105 mmHg and increase ≥15 mmHg from baseline
Pulse rate	≤50 bpm and decrease ≥15 bpm from baseline	≥120 bpm and increase ≥15 bpm from baseline
Respiratory Rate	≤8 brpm and decrease ≥7 brpm from baseline	≥25 brpm and increase ≥7 brpm from baseline
Temperature		≥38.3°C and increase ≥1.1°C from baseline

bpm=Beats per minute; brpm=Breaths per minute.

## 4.8. Immunogenicity

Serum samples will be collected and will be tested for binding anti-AUX-I and anti-AUX-II antibodies. When immunogenicity samples are required on Day 1, the samples will be collected prior to study treatment administration. The samples also will be tested for neutralizing antibodies at times to be determined by the sponsor.

## 5. ANALYSIS POPULATIONS

The study will use the following analysis populations for data summaries.

**Table 18: Analysis Populations**

Population	Definition	Analysis
Safety Population	Safety Population is defined as all enrolled participants who received at least 1 injection of CCH.	All demographic, baseline characteristics and safety parameters will be summarized based on this population.
Intent-to-Treat (ITT)	The Intent-to-Treat (ITT) Population is defined as all enrolled participants who received at least 1 injection of CCH.	
Modified Intent-to-Treat (mITT)	The Modified Intent-to-Treat (mITT) Population is defined as all ITT participants who have at least 1 valid I-GAIS assessment after an injection of CCH.	All efficacy/effectiveness analysis will be based on this population.

## 6. STATISTICAL METHODS

### 6.1. General Methodology

All statistical tests, summary tables and data listings will be prepared using SAS version 9.3 or higher.

All statistical tests will be performed with a significance level of  $\alpha=0.05$ , unless specified otherwise and will be supported by presenting estimates and 95% confidence intervals (CI).

Continuous data will be summarized using descriptive statistics. Discrete data will be summarized using frequency counts and percentages. The denominator will be based on the number of evaluable subjects in the appropriate population.

For the purpose of display, the summary results will be rounded as follows:

- Minimum and maximum: same number of decimal places as the raw data.
- Mean and Median: one decimal place more than the raw data.
- Standard deviation (SD): Two decimal places more than the raw data.
- Percentages will be displayed with one decimal place precision.

For categorical variables with missing values, a category documenting the frequency of missing values will be displayed in the summary tables.

Summary tables, subject listings, graphs and any supportive SAS output will include footnotes that will indicate:

- Date of data extraction.
- Date and time of output generation.
- SAS program name, including the path, which generated the output.

When calculating percentages, the denominator will be based on the number of subjects with non-missing values. If the denominator is expected to change over time, then the denominator used to calculate the percentage will be based on the number of subjects with non-missing values at each visit. Any subject removed from an analysis will be noted at the bottom of the table along with the reason the subject was removed.

Empty summary tables will be presented with a note stating that “No Subjects Met Criteria”.

Subject listings of all data from the eCRFs as well as any derived variables will be presented.

## **6.2. Derived Variables**

[Table 19](#) defines the derived variables for study parameters.

**Table 19: Derived Variables and Definition**

Variable	Definition
Age Group	18 – <35 years 5 – <45 years 45 – 55 years
Height (cm)	If height is recorded in inches, then height is equal to the recorded value multiplied by 2.54 and then rounded to 1 decimal place.
Weight (kg)	If weight is recorded in pounds, then weight is equal to the recorded value multiplied by 0.454 and then rounded to 1 decimal place.
Body Mass Index (BMI)	BMI will be computed using height measured at screening and body weight measured at respective visits as, $BMI (kg/m^2) = Weight (kg) / Height (m)^2$
Relative Day	The day of first injection of study drug will be considered as relative Day 1.
Study Day (for assessment on or after Day 1)	Study Day will be computed as: Date of Assessment – Date of Day 1 + 1
Study Day (for assessment before Day 1)	Study Day will be computed as: Date of Assessment – Date of Day 1
Baseline	Baseline is defined as the last non-missing measurement/assessment prior to the first dose of study drug. For clinical laboratories this will be the screening value. The assessments made in unscheduled visits will be considered in calculation of baseline, if the unscheduled assessment is the closest value preceding the first dose of study drug.
Baseline for Vital Signs on Injection Days	For vital signs on injection days, the baseline value will be the vital sign measure immediately prior to the first dose of study drug.
Change from baseline	Change from baseline will be derived as: post baseline visit/time point value – the baseline value.
Last (analysis)	Last is defined as the last non-missing measurement/assessment post the first dose of study drug.
Last Date in Study	Last date in study is defined as: 
 
• The date of Day 180 Visit if the subject completes the study.
 
• The date of ET visit if the subject is terminated early from study at a non-scheduled visit.
 
• The date of the latest scheduled visit if the subject is terminated early from study at a scheduled visit or lost to follow-up.
 

Age (Years) at cellulite Onset	(Date of cellulite symptoms reported – Date of Birth)/365.25. See Section 6.3.1.3 for handling of partial or unknown Cellulite symptom onset dates.
Time (Years) since last cellulite treatment	(Date of informed consent – Date of most recent cellulite treatment)/365.25. See Section 6.3.1.3 for handling of partial or unknown treatment dates.
Duration (Minutes) of Exposure at each visit	Date/Time of Last Injection – Date/Time of First Injection
Duration (Days) of AE	AE end date – AE start date + 1
AE Start Day	AE start date – Date of Day 1 + 1
AE Stop Day	AE end date – Date of Day 1 + 1

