i Collected after treatment on Study Day 1 and is assessed for the overall subject and not per treatment areas.

j [REDACTED]

k Photographs will be taken before and after marking the treatment areas. [REDACTED]  
[REDACTED] For subjects not receiving treatment during a treatment phase visit a photograph will be taken but no marking will be done and no postmarking photograph will be taken. Please see the Photography Manual for details.

 Subjects will receive at least 3, and up to 6 treatment sessions. The investigator will determine the total number of treatments the subject will receive and can incrementally treat new sub-areas at consecutive treatment phase visits. Specific injection sites (sub-areas) within the overall treatment area will not be dosed more frequently than every 56 days. At the Treatment Phase visits after Day 1, the investigator has the option to skip treatment or proceed with a treatment session for a new sub-area. [REDACTED]

[REDACTED] After treatment subjects will be provided with compression garments that they will be required to wear.

AE=Adverse event; CR-PCSS=Clinician-reported Photonumeric Cellulite Severity Scale; CSS= Cellulite Severity Scale; ECG=Electrocardiogram; I-GAIS=Investigator Global Aesthetic Improvement Scale; S-GAIS=Subject Global Aesthetic Improvement Scale.

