#### **7.8.5. Vital Signs**

Vital signs (systolic and diastolic blood pressure, pulse rate, respiratory rate, and body temperature) will be summarized by treatment regimen and overall using descriptive statistics for observed and change from baseline values for all assessments visits. Baseline (study baseline) will be the vital sign value taken at Day 1 predose for the by-visit analyses.

Vital signs will additionally be summarized by treatment regimen and overall for observed and change from baseline values for all time points on each injection day. For each injection day, baseline (injection day baseline) will be a predose value taken on that day.

The PCI vital signs values will be summarized by treatment regimen and overall using frequency counts and percentages. Refer to [Table 17](#) for PCI criteria.

A subject listing will be presented for vital sign results.

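### Two SAP derivation rules conflict with the SAP's own analysis text, in descriptive tables only: the injection-day vital-sign baseline (Table 19 against 7.8.5) and concomitant status with a partial start date (6.3.1.2 against 4.4)

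*SAP*

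**What the plan says.** **Vital signs.** SAP Table 19 has two relevant rows. The general row reads "Baseline is defined as the last non-missing measurement/assessment prior to the first dose of study drug". The injection-day row reads "For vital signs on injection days, the baseline value will be the vital sign measure immediately prior to the first dose of study drug". SAP 7.8.5 keeps Day 1 predose as the baseline for the by-visit analyses, but for the injection-day summaries it says "For each injection day, baseline (injection day baseline) will be a predose value taken on that day".

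SAP 4.7.2.2 leaves postdose readings out of the by-visit analysis and sends the reader to Table 19 for the definition of baseline. It also holds the PCI rule: "Vital sign values are PCI if they meet both the observed value criteria and the change from baseline criteria". Table 17 gives the limits; for low systolic pressure these are 90 mmHg or less together with a fall of at least 20 mmHg.

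On sessions, SAP Table 2 says "Subjects will receive at least 3, and up to 6 treatment sessions". Vital signs are taken before dosing and at 15 and 30 minutes after it.

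**Concomitant medication.** SAP 4.4 counts any medication used from Screening to Day 180, or still ongoing. It says explicitly that one started before Screening and continuing is both prior and concomitant. The heading and stem of SAP 6.3.1.2 cover start dates that are wholly unknown. Its first bullet makes an ongoing medication with such a date concomitant. Its last bullet deals with start dates that are partly known: if the month and year precede first injection, the medication is not concomitant. That bullet sets no condition on the end date.

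**The concern.** A programmer who takes Table 19 literally and one who follows 7.8.5 will produce different injection-day change summaries from the same data. Change from baseline in vital signs and PCI vital signs are both named among the secondary safety endpoints in SAP Table 1, so the output is a reported one. The predose change on a later injection day is zero by construction under 7.8.5 and generally not zero under Table 19.

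For medications, the last bullet of 6.3.1.2 can remove from the SAP 7.6 concomitant table drugs that subjects were taking during the study. It also has a perverse effect: an ongoing drug with no start date at all is counted, while the same drug with a known start month is not.

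**Working it through.** The plan states no figure on this point, so there is none to reproduce.

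**(a) How often the baselines are different measurements.** Both rules give Day 1 predose at the first session. At every later treated session Table 19 still points to Day 1 and 7.8.5 points to that day. With k treated sessions, the measurements differ at k − 1 of them. With two postdose readings per session:

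| Sessions k | Postdose readings 2k | Readings with a different baseline 2(k − 1) |
|---|---|---|
| 1 | 2 | 0 |
| 3 | 6 | 4 (66.7%) |
| 6 | 12 | 10 (83.3%) |

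This follows from the text alone. Three is the stated minimum, but Protocol 6.3 and 6.8 let the investigator stop treatment at visits after Day 1, so smaller k is possible.

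**(a) Constructed systolic examples (mmHg), Table 17 low rule.**

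| Day 1 predose | Same-day predose | Postdose | Change, Table 19 | Change, 7.8.5 |
|---|---|---|---|---|
| 112 | 105 | 88 | 88 − 112 = −24, PCI | 88 − 105 = −17, not PCI |
| 104 | 112 | 88 | 88 − 104 = −16, not PCI | 88 − 112 = −24, PCI |

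A flag can therefore move either way, if the PCI criterion uses the injection-day baseline. The SAP does not say that it does.

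**(a) Conditional size of the PCI effect.** The documents give no variances, so these are assumptions: systolic mean 115, between-subject SD 12, visit-to-visit SD v and pre-to-postdose SD p each set at 5, 8 or 11, two postdose readings per session, values rounded to 1 mmHg, the systolic low and high rules only, and a subject counted as PCI if any postdose reading is. There were 400,000 simulated subjects per setting, scaled to 32. Expected subjects who are PCI under one baseline only:

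| Sessions | Lowest setting | Highest setting |
|---|---|---|
| 1 | 0 | 0 |
| 2 | 0.16 | 2.33 |
| 3 | 0.31 | 3.95 |
| 6 | 0.70 | 6.91 |

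Variants at 3 to 6 sessions:
- by-visit predose PCI pooled into the same table: 0.29 to 4.91
- identical 15- and 30-minute deviations (v = p): 0.17 to 5.32
- Day 1 systolic limited to 91–139 (v = p): 0.32 to 7.11

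Across all of these the range is 0.17 to 7.11, or about 0.2 to 7 subjects.

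The direction is lopsided. In the middle setting (v = p = 8) at six sessions, 4.43 subjects are discordant, 5.19 are PCI under the Day 1 baseline and 1.23 under the same-day baseline. Let x be flagged only under Day 1 and y only under same-day. Then x + y = 4.43 and x − y = 5.19 − 1.23 = 3.96, so x ≈ 4.2 and y ≈ 0.2. The split is less extreme where p is large relative to v, but the direction is the same.

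**(b) Medication rules side by side.** Constructed dates: Screening 11 Jan 2021, first injection 5 Feb 2021 (25 days later, within the 28-day screening window).

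| Medication | 4.4 | 6.3.1.2 last bullet | 6.3.1.2 if start wholly unknown |
|---|---|---|---|
| Start Mar 2019, ongoing | concomitant | not | concomitant |
| Start Jan 2021 (day missing), ended 20 Feb 2021 | concomitant | not | concomitant |
| Start Mar 2019, ended Apr 2019 | not | not | not |

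A plausible case of the first row is a long-standing oral contraceptive, which is a permitted method in SAP 3.2. The bullet repeats the condition of the adverse-event bullet in 6.3.1.1. That condition suits an event, whose emergent status depends on onset, but not a drug, whose concomitant status depends on use. It also uses first injection as the cut-off where 4.4 uses Screening.

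**The case against.** **Table 19 is loose, not wrong.** A separate injection-day row would be nearly redundant if it meant Day 1, and Table 19 elsewhere uses first injection in a per-visit sense (duration of exposure). Section 7.8.5 defines both baselines, and the PCI summary is specified there, directly after them. This stands as evidence of intent: the same-day value was probably meant. It does not rescue the wording. The general Baseline row gives the same expression its study-level meaning, and 4.7.2.2, which holds the PCI rule, points to Table 19 alone.

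**The PCI counts are speculative.** This stands. A reader might infer that the PCI table will be wrong by several subjects, that same-day predose is the required PCI baseline, or that errors fall equally in both directions. The documents support none of these. No section says which baseline applies to postdose PCI, Day 1 predose is also defensible, the variances are assumed, and under those assumptions the Day 1 baseline mainly flags more. Nor will every change value after the first session differ, since two readings can coincide.

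**The stray bullet is outside its own scope.** Read strictly, 6.3.1.2 covers only wholly unknown start dates, so the bullet never operates and 4.4 decides correctly. That holds if 4.4 is taken to prevail, but the SAP does not say so, and the bullet expressly addresses partial dates. A reader might also infer that medications vanish from the record or that prohibited-medication deviations are missed. The SAP 7.6 listing keeps every record, although its flag could carry the error, and SAP 4.3 does not tie deviations to this flag.

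**Conclusion.** Both conflicts are in the current SAP text, and SAP Table 20 lists no change that explains either. The point is minor.

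(a) What is certain is that the two baselines are different measurements at k − 1 of k treated sessions, so injection-day change values there will generally differ. An effect on PCI counts is conditional on which baseline the sponsor intends. The estimate of about 0.2 to 7 of 32 subjects rests wholly on assumed systolic variances and shows only that the choice can matter.

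(b) The last bullet of 6.3.1.2 contradicts 4.4 and its own section, and can only undercount concomitant use. The number of affected records cannot be derived and may be zero.

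The primary I-GAIS proportion and its interval, the by-visit vital-sign summaries, the on-site safety observation and the listings of raw values are untouched.

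**What to change.** 1. In the injection-day row of SAP Table 19, replace the reference to the first dose with *dosing on that injection day*, so that it matches 7.8.5.
2. Add one sentence to SAP 4.7.2.2 naming the baseline that the Table 17 change criteria use for postdose readings. Same-day predose fits the injection-day analysis in 7.8.5, but the choice is the sponsor's.
3. Replace the last bullet of SAP 6.3.1.2 with: *For a partial start date before first injection, the medication is not concomitant only if the end date is known to be before Screening; otherwise it is concomitant.*
4. In both the heading and the stem of 6.3.1.2, widen the scope to *completely or partly unknown*, so that the section covers the cases its bullets address.

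The cost is a few rewordings and one added sentence in the SAP. No new data are needed.

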### **6.3. Handling of Missing Data**

Subjects who withdraw from the study after the initiation of the study drug will not be replaced and available data for these subjects until the point of withdrawal will be summarized.

The missing baseline assessment will not be imputed.

For categorical variables with missing values, a category documenting the frequency of missing values will be displayed in the summary tables.

For Body Q- Appraisal of Cellulite, if missing data at a visit is less than 50% of the scale's items, the mean of the completed items multiplied by 11 will be used to determine total score. Also, if the missing data at a visit is more than 50% then for that subject raw sum score will be considered as missing.

There will be no imputation of missing values for safety data, however missing relationship between AE and study drug will be considered as related to study drug following worst case principle. Missing severity of an AE will be summarized as a severe AE. Duration of the AE is classified in the '>21 Days' category if an AE is ongoing for more than 21 days by the last visit of the subject in the study.

Immunogenicity samples with a positive titer value will undergo a log transformation for analyses. Samples with titer level less than 10 will be assigned or imputed as a log transformed titer of 1 for analyses.

#### **6.3.1. Imputation of Partial Dates**

##### **6.3.1.1. TEAE Status for Completely Unknown Start Date**

The following rules will apply in cases where start date of an AE is completely unknown:

- If the AE onset date is unknown and the end date is on or after first injection on Day 1 or ongoing, then the AE will be considered a TEAE.
- If the AE onset date is unknown and the end date is before first injection on Day 1, then the AE will not be considered a TEAE.
- If both the start and end dates are unknown (or end date is ongoing), then the AE will be considered a TEAE, following the worst-case principle.
- If the AE onset date is partly present and month/year is prior to the first injection date, then the AE will not be considered a TEAE.

##### **6.3.1.2. Concomitant Status of Medication for Completely Unknown Start Date**

The following rules will apply in cases where start date of concomitant medication is completely unknown:

- If the medication onset date is unknown and the end date is after the screening date but before the Day 180 visit date or the medication is ongoing, then the medication will be considered as concomitant.
- If the medication onset date is unknown and the end date is before the screening date, then the medication will not be considered as concomitant.

- If both the start and end dates are unknown, then the medication will be considered as concomitant. This approach is considered to be the most conservative following the worst-case principle.
- If the medication onset date is partly present and month/year is prior to the first injection date, then the medication will not be considered as concomitant.

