## 6.7. Prior and Concomitant Medications and Procedures

The start and stop date, dose, unit, frequency, route of administration, and indication for all prior (taken within the 30 days prior to the Screening Visit) and concomitant (taken from the Screening Visit through the End of Study Visit) medications and nondrug therapies (eg, blood transfusions, oxygen supplementation, physical therapy, etc) received will be recorded.

In addition, all prior treatments for the disease/condition under study will be recorded with start and stop date, dose, unit, frequency and route of administration.

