## 4.4. Prior/Concomitant Medications

All medications will be coded using World Health Organization (WHO) Drug Dictionary, by active ingredient and WHO anatomical therapeutic chemical (ATC) classification of ingredients.

A prior medication is defined as any medication taken prior to the Screening Visit.

A concomitant medication (or non-drug therapy) is any medication (or therapy) taken on or after the Screening Visit through the Day 180 Visit or the medication is reported as ongoing.

Please note that if a medication started prior to Screening and end date is after Screening/ongoing it will be counted as both prior and concomitant medication.

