## **7.6. Prior/Concomitant Medications and Procedures**

Prior and concomitant medications will be summarized by treatment regimen and overall using frequency counts and percentages by active ingredient within each ATC, with ATC and active ingredients ordered alphabetically. Prior and concomitant procedures (non-drug therapies) will be summarized by treatment regimen and overall using frequency counts and percentages with name of the procedures ordered alphabetically. Multiple uses of the same medication/procedure by a subject will be counted only once.

A subject listing of medications indicating prior and concomitant medications and procedures will be provided. Similarly, a separate listing of medications and procedures for cellulite will also be presented.

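### SAP 6.3.1.2 classes a drug with a partial start date before first injection as not concomitant even if it is still in use, against SAP 4.4 and Protocol 6.7 (minor)

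*SAP*

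**What the plan says.** SAP 4.4 defines a concomitant medication as "any medication (or therapy) taken on or after the Screening Visit through the Day 180 Visit or the medication is reported as ongoing". It adds that "if a medication started prior to Screening and end date is after Screening/ongoing it will be counted as both prior and concomitant medication". Protocol 6.7 uses the same window: sites record "concomitant (taken from the Screening Visit through the End of Study Visit) medications and nondrug therapies". In both places the test is use from Screening onward, and neither sets a condition on when the drug was started.

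SAP 6.3.1.2 deals with incomplete start dates. Its lead-in reads "The following rules will apply in cases where start date of concomitant medication is completely unknown". The first bullet makes a drug with an unknown start concomitant if "the end date is after the screening date but before the Day 180 visit date or the medication is ongoing". The second makes it not concomitant if it ended before Screening. The third makes it concomitant if start and end are both unknown, and cites the worst-case principle. The fourth turns to partial dates: "medication onset date is partly present and month/year is prior to the first injection date, then the medication will not be considered as concomitant".

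The classification feeds SAP 7.6: "Prior and concomitant medications will be summarized by treatment regimen and overall using frequency counts and percentages by active ingredient within each ATC". The same section plans a subject listing that marks prior and concomitant use. SAP Table 20, which lists significant changes from the protocol, has only N/A.

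**The concern.** The fourth bullet differs from the definition in two ways. It looks only at the start date, so a drug taken throughout the study is classed the same way as one stopped years earlier. It also measures from first injection, which can fall up to 28 days after the start of screening (Protocol 5.4), so use between Screening and first injection can be lost too.

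A start known only to the month and year is plausible for long-term medication. Oral contraceptives are among the methods accepted under inclusion criterion 4, and low-dose aspirin is permitted under Protocol 6.7.1. A user of either whose start is recorded as a month and year before first injection would be flagged as not taking the drug concomitantly.

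A programmer cannot satisfy both SAP 4.4 and the fourth bullet for such a record. At stake is the accuracy of a descriptive medication summary and of the flag in the listing.

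**Working it through.** The plan gives no figure to reproduce and no arithmetic decides the point. The check is to apply the three rules to the same records.

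Illustrative dates (assumed): Screening 10 Jan 2021 and first injection 3 Feb 2021. The gap is 24 days, within the 28 allowed.

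| Case | Start | End | SAP 6.3.1.2 | SAP 4.4 | Protocol 6.7 |
|---|---|---|---|---|---|
| 1 | Mar 2018, day unknown | ongoing | not concomitant (bullet 4) | prior and concomitant | concomitant |
| 2 | Mar 2018, day unknown | 15 Apr 2021 | not concomitant (bullet 4) | prior and concomitant | concomitant |
| 3 | Jan 2021, day unknown | 20 Jan 2021 | not concomitant (bullet 4) | concomitant | concomitant |
| 4 | Mar 2018, day unknown | 1 Dec 2020 | not concomitant (bullet 4) | prior only | not concomitant |
| 5 | completely unknown | ongoing | concomitant (bullet 1) | concomitant | concomitant |
| 6 | 15 Mar 2018 | ongoing | not needed | prior and concomitant | concomitant |

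- **Cases 1 and 2** conflict because the fourth bullet ignores the end date.
- **Case 3** shows the effect of the different cut-off: the drug was used after Screening and stopped before first injection.
- **Case 4** shows no conflict. For a drug within its reach, the fourth bullet agrees with the other two rules only when use ended before Screening.
- **Cases 1, 5 and 6** are the same ongoing drug with three qualities of start date. The complete date and the completely unknown date both give concomitant; the partial date does not. Less knowledge of the start gives the answer that SAP 4.4 requires, and a little more knowledge reverses it.

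The wording closely follows the fourth bullet of SAP 6.3.1.1 on adverse events: "AE onset date is partly present and month/year is prior to the first injection date, then the AE will not be considered a TEAE". There, onset relative to first injection is the relevant test. Concomitant status depends on use, so the same test does not carry over. That the sentence was carried across is an inference; the documents do not say so.

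**The case against.** The strongest reply is that SAP 4.4 already settles the case. A drug started in March 2018 and ongoing meets its definition with no imputation, because the month and year are enough to place the start before Screening. The heading and lead-in of 6.3.1.2 confine the list to completely unknown start dates, so the fourth bullet could be treated as a stray line. This supports a low grading but does not remove the conflict. The bullet names partly present dates expressly, SAP 4.4 claims no precedence over it, and Table 20 declares no departure from the protocol. A condition that the drug must also have ended before Screening could be read in, but none is written, although the first two bullets do state end-date conditions.

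A reader might infer that affected drugs vanish from the outputs. The documents do not support that. Most would still count as prior medications, and all stay in the listing. SAP 7.6 does not say whether prior and concomitant use are tabulated separately; in a combined table, a drug counted as prior would remain visible.

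A reader might also infer that prohibited anticoagulant or antiplatelet use could go unnoticed. That does not follow either. Under SAP 4.3, deviations may be derived from case report form data, vendor data and monitoring reports, and Protocol 6.7.1 sends prohibited use straight to the medical monitor. Neither depends on this flag.

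**Conclusion.** The point stands as a minor error: the rule is wrong as written, not merely short of detail. Followed literally, it gives a concomitant status that contradicts SAP 4.4 and Protocol 6.7 for any drug with a partial start before first injection that was still in use at or after Screening.

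The effect is limited to a possible undercount of concomitant medications in the SAP 7.6 summary and a wrong flag in the listing. Its size cannot be derived, because the documents do not say how many start dates will be partial; the number may be zero. The primary I-GAIS responder proportion, its confidence interval, the other efficacy endpoints and the counts of treatment-emergent adverse events do not use this classification and are unchanged. The conclusion assumes only that the fourth bullet is applied as worded.

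**What to change.** Widen the heading and lead-in of SAP 6.3.1.2 to cover an unknown or partial start date, and replace the fourth bullet with:

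> *For a partial start date apply Section 4.4: the medication is concomitant if it is ongoing or its end date is on or after Screening, unknown, or partial and not clearly before Screening; it is not concomitant only if the end date is before Screening.*

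This takes the SAP's own definition as the rule, restores Screening as the cut-off, and covers partial end dates that straddle Screening. Because it refers to Section 4.4, the Day 180 limit there carries over. The cost is one heading, one lead-in and one sentence, plus a small change to the program that derives the flag. No data collection changes.
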